11.4.4 Per-protocol analysis population

Sub-analyses may then be performed on the basis of a subset of ITT population, excluding those for whom major protocol deviations have been identified (e.g., early death due to other reasons, early discontinuation of treatment, major protocol violations, etc.). However, these sub-analyses

may not serve as the basis for drawing conclusions concerning treatment efficacy, and the reasons for excluding patients from the analysis should be clearly reported.

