4.3 Randomization

Patients will be randomized in a 2:1 ratio to receive either CSA or placebo (no CSA). Randomization will be open-label, using the permuted block method and will be stratified by age (<60 or >60 years), WHO severity (4 vs. 5), presence or absence of comorbidities (at least one of the following – hypertension, coronary artery disease, congestive heart failure, or diabetes). Randomization will be performed centrally at the Baylor College of Medicine by the Project Manager.

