10. MEASUREMENT OF EFFECT

The primary outcome of this study is the WHO COVID-19 clinical severity scale on day 14. Please, see the Table 2.

Table 2. WHO COVID-19 Ordinal Outcomes Scale

Patient State	Descriptor	Score
Uninfected	No clinical or virological evidence of infection	0
Ambulatory	No limitation of activities	1
	Limitation of activities	2
Hospitalized Mild disease	Hospitalized, no oxygen therapy	3
	Oxygen by mask or nasal prongs	4
Hospitalized Severe Disease	Non-invasive ventilation or high-flow oxygen	5
	Intubation and mechanical ventilation	6
	Ventilation + additional organ support – pressors, RRT, ECMO	7
Dead	Death	8

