11.4 Populations for Analysis

11.4.1 Safety population

All patients will be evaluable for toxicity from the time of their first treatment with Neoral and throughout the study period. In this study, patients will receive 7 days of Neoral and incidence of Neoral-associated toxicity events (see 11.5) and all AEs will be assessed daily.

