11.4.2 Intent to treat (ITT) population

All randomized patients in the study will be assessed for response to treatment, even if there are major protocol treatment deviations. Each patient will be assigned one of the WHO COVID scale categories outlined in **Table 2**. Primary and secondary objectives will be analyzed.

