11.5 Analysis of Secondary Endpoints

The secondary objectives are mostly concerned with the safety and effects of Neoral (CSA) in this patient population. The secondary endpoints include Neoral-associated toxicity events, serum inflammatory markers (CRP, d-dimer, ferritin, ANC, absolute lymphocyte count, WBC, PLT (daily while inpatient and including day 14 and 28 for those discharged), Viral load (days 14 and 28), vital status (days 14 and 28), disease improvement (days 14 and 28), proportion of those requiring invasive mechanical ventilation, incidence of deep vein thrombosis, proportion of patients discharged on day 28, time to hospital discharge, and disease resolution (days 14 and 28).

For safety, Neoral-associated toxicity events include nephrotoxicity, resistant hypertension, hepatotoxicity, signs of CNS toxicity, or superinfection. AE's and SAE's by CTCAE v5 will be summarized descriptively with frequencies and rates. Rates and 95% CI's of grade 3 and above AE's will be reported.

Serum inflammatory markers are viewed as interval scales and after appropriate normalizing transformation (if needed), will be analyzed using general linear mixed models to account for within patient dependencies to allow comparisons between groups.

Viral positivity between groups at days 14 and days 28 will be tested by Wilcoxon rank sum test.

Survival analysis methods will be used to describe overall survival experience, to estimate survival at selected time points, and to compare groups. Cumulative incidence analysis methods will be used if there are competing risks. The same approach will be used with disease improvement (alive and free invasive or non-invasive mechanical ventilation) and disease resolution (alive and discharged home without oxygen).

Fisher's exact test will be used to compare rates of need for invasive mechanical ventilation bench marked to a particular time, and ever need. If required, this endpoint will include deaths before intubation in the rare cases in which this occurs.

In exploratory analyses, we will use logistic regression to model ventilator need as a function of treatment group and other baseline characteristics. Survival analysis methods will be used to analyze time to mechanical ventilation, with censoring at last follow-up for those not needing ventilation.

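### Section 11.4.4 treats some early deaths as protocol deviations, so the optional per-protocol comparison is selected on the worst value of the primary endpoint

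*Combined protocol and SAP*

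**What the plan says.** Section 11.4.4 describes a per-protocol subset of the ITT population. It leaves out patients for whom "major protocol deviations have been identified (e.g., early death due to other reasons, early discontinuation of treatment" or other major violations are found. The analysis is optional ("Sub-analyses may then be performed on the basis of a subset of ITT population"), and the section adds that such sub-analyses "may not serve as the basis for drawing conclusions concerning treatment efficacy, and the reasons for excluding patients" must be clearly reported.

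Section 10 states: "The primary outcome of this study is the WHO COVID-19 clinical severity scale on day 14". In Table 2 of that section death is score 8, the highest category.

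Section 4.3 says "Randomization will be open-label, using the permuted block method", and the note in section 6.1 explains that placebo capsules were not feasible. The documents do not define when a death is early or what its reason must be other than, and they provide no blinded adjudication of cause of death.

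The ITT rule in section 11.4.2 goes the other way: "All randomized patients in the study will be assessed for response to treatment, even if there are major protocol treatment deviations". Each patient there receives a WHO category.

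**The concern.** A protocol deviation is a departure from what the protocol asked for. Dying is not one; here it is the worst result the primary endpoint can record. A rule that removes some deaths therefore selects patients on the outcome being compared.

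The selection depends on a judgement made after randomisation, by people who know the arm, against undefined terms. If that judgement removes deaths in equal proportion from both arms, the null comparison is not distorted. If it removes proportionately more Neoral deaths, the comparison shifts towards Neoral.

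A second route lies in the same list. Early discontinuation of treatment is also an excluding deviation, and Arm B has no study agent to discontinue. A Neoral patient who dies before day 7 could be removed under that item even if the early-death item were deleted; a control patient who dies on the same day could not.

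What is at stake is the usefulness of the per-protocol result as a check on the ITT result.

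**Working it through.** **Inputs from the plan.** Section 11.2 and Table 3: 25 control and 50 CSA patients; Wilcoxon rank-sum test, one-sided 10%; control distribution for scores 1 to 8 of 23, 24, 10, 5, 5, 8, 8 and 17%; Scenario 1 power 81% at P1 = 0.65.

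**Assumptions.** The share f of deaths excluded in each arm, and a 25% Neoral death rate in the harm case. The documents give no figure for either.

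**Step 1: reproduce the plan's figure.** P1 = Pr(Control > CSA) + ½·Pr(tie). For Scenario 1 this is 0.5466 + 0.1037 = 0.650. The normal approximation gives power Φ[(0.650 − 0.5)·√(12·25·50/76) − 1.2816] = 79.7%. Simulation of the tie-corrected test gives 82.8%. Both are within 2 points of the stated 81%, so the test is understood correctly.

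**Step 2: shift in P1 under no effect.** Put the control distribution in both arms. Expected Neoral deaths are 50 × 0.17 = 8.5. A control patient compared with a Neoral death scores ½ × 0.17 = 0.085. Removing a share f of Neoral deaths only gives

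P1(f) = (0.5 − 0.17f × 0.085) / (1 − 0.17f).

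For f = 50%: (0.5 − 0.007225) / 0.915 = 0.539.

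**Step 3: rejection rate in the per-protocol set.** Simulation with the tie-corrected test, rejecting when z > 1.2816:

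| Neoral deaths excluded | Control deaths excluded | Neoral deaths removed, expected | P1 | Rejection |
|---|---|---|---|---|
| 0% | 0% | 0 | 0.500 | 10% |
| 12% | 0% | 1.0 | 0.509 | about 13% |
| 25% | 0% | 2.1 | 0.518 | 16% |
| 50% | 25% | 4.25 | – | 16% |
| 50% | 0% | 4.25 | 0.539 | 24% |
| 50% | 50% | 4.25 | 0.500 | 10% |

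The rule covers both arms, so the bias can also run the other way. By symmetry, dropping 50% of control deaths and no Neoral deaths gives P1 = 1 − 0.539 = 0.461, against Neoral.

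**Step 4: harm case (assumed 25% versus 17% deaths).** If the extra 8 points come equally from scores 1 and 2, P1 = 0.5 + 0.08 × 0.085 − 0.04 × 0.885 − 0.04 × 0.65 = 0.445. Dropping half the Neoral deaths and no control deaths gives (0.4454 − 0.125 × 0.085) / 0.875 = 0.497. If the extra deaths come proportionally from all other scores, P1 goes from 0.460 to (0.460 − 0.125 × 0.085) / 0.875 = 0.514. Either way the signal is lost in this one set at that assumed share.

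**The case against.** The strongest reply is that nothing important rests on this analysis. Section 11.4.4 makes it optional, bars efficacy conclusions from it and requires the reasons for exclusion to be reported. The rejection rates above are therefore not error rates of the trial. That stands, and it sets the severity.

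A reader might infer that the rule lets the trial hide drug-related deaths. The documents do not support that:
- ITT keeps every randomised patient and assigns a WHO category (11.4.2).
- Survival is compared between groups, with vital status at days 14 and 28 (11.5), and death is its own category in the day-28 discharge analysis.
- The safety set has no exclusion by cause of death: "All patients will be evaluable for toxicity from the time of their first treatment with Neoral and throughout the study period" (11.4.1).
- Any Neoral death judged at least possibly related pauses accrual for DSMB review (11.6.1).
- Mortality is followed to day 60 (section 12), and deaths within 30 days of the last dose get expedited reporting whatever the cause (12.3.1).

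A reader might also infer that fatal superinfections on Neoral would be filed under other reasons. That is one reading of an undefined phrase. Section 11.5 says "Neoral-associated toxicity events include nephrotoxicity, resistant hypertension, hepatotoxicity, signs of CNS toxicity, or superinfection", which weighs against calling such a death unrelated to treatment.

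The size is also open to challenge. The 24% figure needs about 4 of 8.5 Neoral deaths to be classed as early and unrelated, with no control death so classed. With about one such death the rate is about 13%.

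What survives is narrower. The rule as written selects on the outcome, and reporting the exclusions does not remove the bias from the estimate.

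**Conclusion.** The point holds as a minor but clear error in a supportive analysis. Under no effect, rejection in the per-protocol set rises from 10% to about 13%, 16% or 24% when 12%, 25% or 50% of Neoral deaths and no control deaths are excluded, and does not rise when the shares are equal. The inflation therefore depends wholly on differential exclusion. The shares are assumptions, and the lower end is the more plausible if clearly unrelated deaths are rare. The base rate of 17% deaths is the plan's own.

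The documents do not support extending this to the ITT result, or to a claim that the trial as a whole could conceal a mortality excess. The loss of the harm signal in step 4 is confined to the per-protocol set.

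**What to change.** In section 11.4.4:
- Delete the early-death example from the list of major deviations.
- Add that no patient leaves the per-protocol set because of death, including a death before day 7 that would otherwise count as early discontinuation of treatment. Deleting the example alone would leave that second route open for the Neoral arm only.
- State that every death by day 14 keeps score 8 whatever its cause, and that cause of death is reported descriptively by arm.

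The cost is a sentence or two of text, with no extra data, visits or patients. The downside is that a rare, clearly unrelated death stays in the per-protocol set, as it already does in ITT.

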11.5 Analysis of Secondary Endpoints

The secondary objectives are mostly concerned with the safety and effects of Neoral (CSA) in this patient population. The secondary endpoints include Neoral-associated toxicity events, serum inflammatory markers (CRP, d-dimer, ferritin, ANC, absolute lymphocyte count, WBC, PLT (daily while inpatient and including day 14 and 28 for those discharged), Viral load (days 14 and 28), vital status (days 14 and 28), disease improvement (days 14 and 28), proportion of those requiring invasive mechanical ventilation, incidence of deep vein thrombosis, proportion of patients discharged on day 28, time to hospital discharge, and disease resolution (days 14 and 28).

For safety, Neoral-associated toxicity events include nephrotoxicity, resistant hypertension, hepatotoxicity, signs of CNS toxicity, or superinfection. AE's and SAE's by CTCAE v5 will be summarized descriptively with frequencies and rates. Rates and 95% CI's of grade 3 and above AE's will be reported.

Serum inflammatory markers are viewed as interval scales and after appropriate normalizing transformation (if needed), will be analyzed using general linear mixed models to account for within patient dependencies to allow comparisons between groups.

Viral positivity between groups at days 14 and days 28 will be tested by Wilcoxon rank sum test.

Survival analysis methods will be used to describe overall survival experience, to estimate survival at selected time points, and to compare groups. Cumulative incidence analysis methods will be used if there are competing risks. The same approach will be used with disease improvement (alive and free invasive or non-invasive mechanical ventilation) and disease resolution (alive and discharged home without oxygen).

Fisher's exact test will be used to compare rates of need for invasive mechanical ventilation bench marked to a particular time, and ever need. If required, this endpoint will include deaths before intubation in the rare cases in which this occurs.

In exploratory analyses, we will use logistic regression to model ventilator need as a function of treatment group and other baseline characteristics. Survival analysis methods will be used to analyze time to mechanical ventilation, with censoring at last follow-up for those not needing ventilation.

Day 28 discharge will be trichotomized as death prior to day 28, discharge by day 28, hospitalized after day 28. Groups will be compared using Chi square test for independence.

Survival analysis methods will be used with death prior to discharge considered as a competing risk.

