6.2 General Concomitant Medication and Supportive Care Guidelines

Because there is a potential for interaction of Neoral with other concomitantly administered drugs, the case report form must capture the concurrent use of all other drugs, over-the-counter medications, or alternative therapies. The Principal Investigator should be alerted if the patient is taking any agent known to affect or with the potential for drug interactions. The study team should check a frequently-updated medical reference for a list of drugs to avoid or minimize use of (shown below). Patients in this study may receive Neoral in combination with other standard of care agents for COVID-19. These include Remdesivir and Dexamethasone. Adverse drug interactions between Neoral and these agents are not described but will be rigorously monitored.

The data that follow are also found in the USPI for Neoral (https://www.accessdata.fda.gov/drugsatfda_docs/label/2019/050715s035,050716s038lbl.pdf):

6.2.1 Drug Interactions: Effect of Drugs and Other Agents on Cyclosporine Pharmacokinetics and/or Safety

6.2.1.1 **Renal Impairment:** All of the individual drugs cited below are well substantiated to interact with cyclosporine. In addition, concomitant non-steroidal anti-inflammatory drugs, particularly in the setting of dehydration, may potentiate renal dysfunction.

Drugs That May Potentiate Renal Dysfunction

Antibiotics	Antineoplastics	Antifungals	Anti-inflamatory Drugs	Gastrointestinal Agents	Immunosuppressives	Other Drugs
ciprofloxacin	melphalan	amphotericin B	azapropazon	cimetidine	tacrolimus	fibric acid derivatives (e.g., bezafibrate, fenofibrate)
gentamicin		ketoconazole	colchicine	ranitidine		methotrexate
tobramycin			diclofenac			
vancomycin			naproxen			
trimethoprim with sulfamethoxazole			sulindac			

During the concomitant use of a drug that may exhibit additive or synergistic renal impairment with cyclosporine, close monitoring of renal function (in particular serum creatinine) will be

performed. If a significant impairment of renal function occurs, the dosage of the co-administered drug should be reduced or an alternative treatment considered.

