8. STUDY CALENDAR

Table 1 Schedule of Study Events (Part 1)

Visit	Screening	Baseline	Treatment ¹							Follow-up ²		
	1	2	3	4	5	6	7	8	9	10		
Study Day	-21 to -1	-2 to 0	1	2	3	4	5	6	7	8	9	10
Written Informed Consent	X											
Assign Screening Number	X											
Complete Medical History	X											
Demographics	X											
Inclusion/Exclusion Criteria Review	X											
WHO COVID-19 Severity Scale	X	X	X	X	X	X	X	X	X	X	X	X
Assign Enrollment Number		X										
Complete Physical Examination	X	X	X	X	X	X	X	X	X	X	X	X
Vital Signs (BP, HR, RR, Temp, SpO ₂)	X	X	X	X	X	X	X	X	X	X	X	X
FIO ₂ Assessment	X	X	X	X	X	X	X	X	X	X	X	X
Pregnancy Test for Female Patients	X											
Cyclosporine Administration			X	X	X	X	X	X	X			
12-Lead ECG	X								X			X
Chest X-ray	X								X			X
BMP	X	X	X	X	X	X	X	X	X	X	X	X
LFTs	X	X	X	X	X	X	X	X	X	X	X	X
CBC	X	X	X	X	X	X	X	X	X	X	X	X
ANC	X	X	X	X	X	X	X	X	X	X	X	X
Absolute Lymphocyte Count	X	X	X	X	X	X	X	X	X	X	X	X
Total Cholesterol	X	X										
Ferritin	X	X	X	X	X	X	X	X	X	X	X	X
D-Dimer	X	X	X	X	X	X	X	X	X	X	X	X
CRP	X	X	X	X	X	X	X	X	X	X	X	X
LDH	X	X	X	X	X	X	X	X	X	X	X	X
Magnesium	X	X	X	X	X	X	X	X	X	X	X	X
Phosphorus	X	X	X	X	X	X	X	X	X	X	X	X
PT/PTT	X	X							X			
SARS-CoV-2 PCR	X											
AE Assessment	Continuous Monitoring from Signing of the Informed Consent-----►											
Concomitant Medications/Therapies	Continuous Monitoring from Signing of the Informed Consent-----►											

ANC =Absolute neutrophil count; BMP =basic metabolic panel; BP = blood pressure; CBC = complete blood count; CRP =c-reactive protein; ECG = Electrocardiogram; FIO₂ = oxygen requirement; HR = heart rate; LDH = lactate dehydrogenase; LFTs = liver function tests; PT = prothrombin time; PTT = partial thromboplastin time; RR = respiratory rate; SpO₂ = oxygen saturation; WHO = World Health Organization.

¹Treatment assessments will be performed every 24±6 hours. Treatment is Neoral for 7 days and will discontinued on the day of discharge if the patient is discharged before the 7d course is completed. If the patient is discharged before 7 days, the patient will not undergo any assessments until the first outpatient visit.

²Follow up will be performed every 24±6 hours while inpatient. Once patient is discharged, follow up will be at days 14±3 days, 28±3 days, and 60±3 days either by in person clinic visit or telemedicine visit.

Table 1 Schedule of Study Events (Part 2)

Visit	Follow-up ²							
	11	12	13	14	15-27	28	60	
Study Day	11	12	13	14	15-27	28	60	

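### Section 11.5 plans no between-arm estimate from the creatinine and ALT/AST values already scheduled in both arms: a minor, low-cost improvement

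*Combined protocol and SAP*

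**What the plan says.** Section 11.5 makes Neoral-associated toxicity events a secondary endpoint and names nephrotoxicity and hepatotoxicity among them. The planned analysis is that "AE's and SAE's by CTCAE v5 will be summarized descriptively with frequencies and rates", and that "Rates and 95% CI's of grade 3 and above AE's will be reported". No contrast between arms is stated.

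The same section treats the inflammatory markers (CRP, d-dimer, ferritin, ANC, lymphocytes, WBC, platelets) differently: they "will be analyzed using general linear mixed models to account for within patient dependencies to allow comparisons between groups". Creatinine, ALT and AST are not on that list.

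Table 1 in section 8 schedules BMP and LFTs at screening, at baseline, daily while inpatient and at day 28, without restricting them to one arm. Its first footnote limits this: "If the patient is discharged before 7 days, the patient will not undergo any assessments until the first outpatient visit". That visit is at day 14 ± 3, in person or by telemedicine.

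On populations, 11.4.1 states: "All patients will be evaluable for toxicity from the time of their first treatment with Neoral". Arm B receives none. Section 11.4.2, however, covers primary and secondary objectives in all randomized patients, and Table 1 collects adverse events by "Continuous Monitoring from Signing of the Informed Consent".

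**The concern.** Renal dysfunction comes first in the list of likely Neoral harms in 12.1.1.3, and renal and liver toxicity are Table 4 targets. Patients hospitalised with COVID-19 can have renal and liver changes without Neoral, and the randomized control arm is what can separate drug from disease. The plan has that arm and the laboratory values, but states no comparison of them.

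A moderate shift, mostly below grade 3, would appear in the tables only if someone recorded it as an adverse event. In an open-label trial the recorder knows the arm. The Table 4 rule does not fill the gap, because it counts grade 3 or higher events against a fixed acceptable rate of 20%, not against control.

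What is at stake is information for a later trial on dose and monitoring. The primary endpoint, the pause rule and the protection of individual patients are unaffected. Section 6.2.1.1 already requires renal monitoring of patients on interacting drugs.

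**Working it through.** **The plan's own safety figures.** An exact binomial recursion over the 50 boundaries in Table 4 gives crossing probabilities of 4.8%, 39.3% and 86.4% at true grade 3+ rates of 20%, 30% and 40%. Section 11.6.2 states at most 5%, 40% and 86%, so these reproduce. The rule is sound for its purpose; it does not compare arms.

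**Inputs.** The allocation of 50 Neoral and 25 control is from 11.2. Two-sided 5% is a choice made here. The documents give no SD, shift size, control event rate or baseline correlation, so all of these are assumptions, with results in SD units.

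**Any-grade category.** A control rate p0 fixes a threshold on a normal scale, and a shift of d SD gives the Neoral rate p1 = 1 − Φ(Φ⁻¹(1 − p0) − d). Power is by exact enumeration of the 50:25 table.

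| p0 | p1 at d = 0.5 | chi-square | Fisher | chi-square, d = 0.3 | Fisher, d = 0.3 |
|---|---|---|---|---|---|
| 10% | 21.7% | 23% | 18% | 10% | 7% |
| 20% | 36.6% | 30% | 28% | 13% | 11% |
| 30% | 49.0% | 37% | 32% | 16% | 13% |
| 40% | 59.7% | 40% | 33% | 18% | 14% |

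**Comparing the values.** With one value per patient, adjusted for a baseline value with correlation ρ, the effect is d/√(1 − ρ²) and power comes from the noncentral t distribution. The 95% CI half-width is t × √(1/n₁ + 1/n₀) × √(1 − ρ²). At 50:25 and ρ = 0 this is 1.993 × 0.245 = 0.488 SD (72 df).

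| Contributing | ρ | Power, d = 0.5 | Power, d = 0.3 | Half-width |
|---|---|---|---|---|
| 50:25 | 0 | 52% | 23% | 0.49 SD |
| 50:25 | 0.5 | 64% | 29% | 0.42 SD |
| 50:25 | 0.7 | 80% | 40% | 0.35 SD |
| 40:20 | 0 | 44% | 19% | 0.55 SD |
| 40:20 | 0.5 | 55% | 24% | 0.48 SD |
| 40:20 | 0.7 | 71% | 33% | 0.39 SD |

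Every half-width exceeds 0.3 SD, so an estimate of zero would not exclude a 0.3 SD shift.

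**Shift table.** This is a binary contrast, so its power is that of the first table: about 30% at 20% v 36.6%. For illustration, 18/50 v 5/25 is 36% − 20% = 16 points, Newcombe 95% CI −7 to 34.

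**Bias in a model of inpatients**, for a true shift of 0.50 SD:
- *Dropping values after renal replacement therapy (RRT).* If RRT removes the top 2% or 5% of control values, the same threshold removes 6.0% or 12.6% on Neoral. Truncated-normal means then give 0.42 or 0.37.
- *A renal rise delays discharge.* Simulation with 40% of controls discharged and discharge depending on severity plus 0.3 or 0.6 times the renal change gives about 0.48 or 0.43.
- *Neoral speeds discharge.* With 40% of controls and 55% on Neoral discharged on severity alone, and a severity-renal correlation of 0.3 or 0.5, the shift appears as about 0.57 or 0.62.

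Discharge can therefore bias the estimate in either direction; excluding values after RRT biases it toward no harm.

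**The case against.** The strongest reply is that nothing here is an error. Objective 1.2.1 frames safety in terms of adverse events, and the tables in 11.5 match it. Nephrotoxicity and hepatotoxicity are already named endpoints, 11.4.2 applies secondary objectives to all randomized patients, and frequencies in a two-arm trial can be shown by arm. Extra laboratory analyses in a 75-patient phase IIa trial are then partly a matter of preference. This stands as far as it goes, and it is why the point is an improvement only. What remains is that 11.5 states no contrast and that the values themselves are never analysed.

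A second reply is that the shift table brings no gain in power and that inpatient data after day 1 are selective. Both are correct. The power gain belongs to the model alone, and the model needs its limits stated.

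A third is that adverse events are graded by CTCAE v5, whose content lies outside the documents, so how far recording a laboratory change depends on judgement cannot be established. This also stands: dependence on open-label recording is a possibility, and its size is unknown.

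A reader might infer from 11.4.1 that control-arm adverse events are not collected or analysed. The documents do not support that. Collection runs from consent without distinction by arm, and 11.4.2 includes all randomized patients. The gap is a missing start point in one definition and would not merit a point alone.

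**Conclusion.** The point holds as a minor, inexpensive improvement. Section 11.5 leaves scheduled renal and hepatic values without a control-referenced estimate, although these are the organ toxicities the protocol itself names.

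For an assumed 0.5 SD shift with all 75 patients contributing, comparing values raises power from 23-40% to 52-80%. For 0.3 SD the rise is from 10-18% to 23-40%. The first figure in each pair is for chi-square; Fisher gives less. These are best cases: they fall with early discharge and rest on assumed shifts, rates and correlations. Reading BMP and LFTs as containing creatinine and ALT/AST is standard and fits 6.2.1.1 and exclusion 3.2.3.

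A reader might also infer that the trial is unsafe or that renal harm goes unmonitored. That does not follow: patients have daily inpatient tests, trough-based dose reduction and a pause rule whose stated properties reproduce.

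**What to change.** Add to 11.5:

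1. The mixed model already planned for inflammatory markers, applied to log creatinine, log ALT and log AST over days 1-7 with the Baseline-visit value as covariate. Report the Neoral/control ratio and 95% CI as an estimate, without a multiplicity claim. Tabulate by arm and day who contributes and why others do not (discharge, death, RRT).
2. By-arm shift tables of each patient's worst value from day 1 to day 7 while inpatient, relative to baseline. Derive them from the laboratory values whether or not an adverse event was recorded, with RRT as the worst renal category. Pre-specify one category per test, give its difference with 95% CI, and show the number of draws by arm, since a longer stay gives more chances of a high value. If eGFR is used, name one of the three Appendix B formulas in advance.
3. A statement that the model describes inpatients only; that differential discharge can bias it toward no harm (a renal rise delays discharge) or away from it (Neoral speeds discharge); that excluding values after RRT pulls it toward no harm; and that a null result does not exclude a moderate shift.

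As an accompanying wording correction, let 11.4.1 start safety evaluability for control patients at study day 1 or randomization.

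The cost is SAP text, a few tables and one existing model run on three more variables. No samples, visits or patients are added. The downside is limited interpretability after early discharge, when treatment and daily tests stop.
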